6.6.3.3.2 Treatment interruptions

For the definition of off-treatment periods an incomplete start or end date for a treatment interruption will be imputed the same way as specified for time-to-event analyses in [Section 6.6.2.2](#). For duration of interruption no imputation will be applied, i.e. interruptions with missing or incomplete start or end date will have duration missing. Overall duration of interruptions per patient will be missing in these cases as well.

6.7 BASELINE, TIME WINDOWS AND CALCULATED VISITS

As a general rule, the last assessment/measurement observed prior to start of trial medication will be used as baseline. If the time of the assessment/measurement was not captured, and it was on the same day trial medication started, it will be assumed that it was taken prior to the intake of trial medication. For the nintedanib-exposure period, the last measurement prior to the first nintedanib intake was defined as the baseline measurement.

Visit windowing will be performed as described in the following tables, in order to assign data to the relevant study visit based on the actual day of the assessment. Data will be analyzed using the re-calculated visits in the statistical tables. However, in the listings, all visits performed will be displayed (even if outside time-window), along with the re-calculated visit.

Exception:

to account for the short timespan between planned visit 6 (with first open-label intake) and visit 7, a special rule is applied to analyses by visit (not cumulative across visits) in case assignment to visit windows leads to missing values at visit 6 or subsequent visit to take possible multiple measurements in the respective other time window into account.

If such an assessment lies in analysis visit window of visit 7, but not later than 1 month after the planned day of visit 7 and still within the double-blind period, then it is allocated to the analysis visit 6.

Similarly, if such an assessment lies in analysis visit window of visit 6, but after the planned day of visit 6 and not within the double-blind period, then it is allocated to the subsequent visit where this assessment is planned.

If after windowing of visits at baseline, two or more values fall within the same baseline interval, then the last value prior to first drug intake will be taken into account. If after windowing of post-baseline visits, two visits fall in the same interval, then the measurement closest to the planned visit will be taken into account. If only on-treatment values are to be considered, this rule will be applied to on-treatment assessments only. In case two measurements are equidistant from the planned visit, then the last one will be picked.

Table 6.7: 1 Time windowing rules for FVC, SpO₂, missed school days, vital signs (syst. and diast. blood pressure, pulse rate) and laboratory tests (incl. LDH)

Time window of actual day ^[1,2]			Allocated to		
Start day	End day (included)	Length of the time-window [days]	Visit number	Visit name	Planned day of the visit
-84	1	85	2	Baseline	1
2	29	28	3	2 weeks	15
30	64	35	4	6 weeks	43
65	127	63	5	12 weeks	85
128	176	49	6	24 weeks	169
177	218	42	7	26 weeks	183
219	309	84	8	36 weeks	253
310	407	112	9 (p)	52 weeks	365 (V _p)
(V _p + 1) + (V _{p+1} - V _p)/2	V _{p+1} + (V _{p+2} - V _{p+1})/2	(V _{p+2} - V _p)/2	p+1		V _{p+1} = V _p + 12 x 7
...	Every 12 weeks thereafter	...

V_p denotes the planned day of the visit

^[1] First trial drug intake date is taken into account as reference to calculate time windows

^[2] Only for LDH biomarker analyses: Biomarker values are only considered up to + 7 days after last drug intake.

Table 6.7: 2 Time windowing rules for weight

Time window of actual day ^[1]			Allocated to		
Start day	End day (included)	Length of the time-window [days]	Visit number	Visit name	Planned day of the visit
-84	1	85	2	Baseline	1
2	29	28	3	2 weeks	15
30	64	35	4	6 weeks	43
65	127	63	5	12 weeks	85
128	211	84	6	24 weeks	169
212	309	84	8	36 weeks	253
310	407	112	9 (p)	52 weeks	365 (V _p)
(V _p + 1) + (V _{p+1} - V _p)/2	V _{p+1} + (V _{p+2} - V _{p+1})/2	(V _{p+2} - V _p)/2	p+1		V _{p+1} = V _p + 12 x 7
...	Every 12 weeks thereafter	...

V_p denotes the planned day of the visit

^[1] First trial drug intake date is taken into account as reference to calculate time windows

Table 6.7: 3 Time windowing rules for height and leg length

Time window of actual day ^[1]			Allocated to		
Start day	End day (included)	Length of the time-window [days]	Visit number	Visit name	Planned day of the visit
-84	1	85	2	Baseline	1
2	127	126	5	12 weeks	85
128	211	84	6	24 weeks	169
212	309	98	8	36 weeks	253
310	449	140	9 (p)	52 weeks	365 (V _p)
(V _p + 1) + (V _{p+1} - V _p)/2	V _{p+1} + (V _{p+2} - V _{p+1})/2	(V _{p+2} - V _p)/2	p+1		V _{p+1} = V _p + 24 x 7
...	Every 24 weeks thereafter	...

V_p denotes the planned day of the visit

^[1] First trial drug intake date is taken into account as reference to calculate time windows

Table 6.7: 4 Time windowing rules for dental examination and bone imaging

Time window of actual day ^[1]			Allocated to		
Start day	End day (included)	Length of the time-window [days]	Visit number	Visit name	Planned day of the visit
-84	15	99	2	Baseline ^[2]	1
16	127	112	5	12 weeks	85
128	211	84	6	24 weeks	169
212	309	98	8	36 weeks	253
310	449	140	9	52 weeks	365 (V_p)
450	617	168	11 (p)	76 weeks	533
$(V_p + 1) +$ $(V_{p+1} - V_p)/2$	$V_{p+1} +$ $(V_{p+2} - V_{p+1})/2$	$(V_{p+2} - V_p)/2$	p+1	100 weeks	$V_{p+1} =$ $V_p + 24 \times 7$
...	Every 24 weeks thereafter	...

V_p denotes the planned day of the visit

^[1] First trial drug intake date is taken into account as reference to calculate time windows

^[2] For assessments in baseline window: if available prior to first trial drug intake, use the latest one of those. If only assessments available after first trial drug intake, use the one closest to the planned day as baseline value.

Table 6.7: 5 Time windowing rules for dental imaging

Time window of actual day ^[1]			Allocated to		
Start day	End day (included)	Length of the time-window [days]	Visit number	Visit name	Planned day of the visit
-84	15	99	2	Baseline ^[2]	1
16	267	252	6	24 weeks	169
268	533	266	9 (p)	52 weeks	365 (V _p)
(V _p + 1) + (V _{p+1} - V _p)/2	V _{p+1} + (V _{p+2} - V _{p+1})/2	(V _{p+2} - V _p)/2	p+1		V _{p+1} = V _p + 48 x 7
...	Every 48 weeks thereafter	...

V_p denotes the planned day of the visit

^[1] First trial drug intake date is taken into account as reference to calculate time windows

^[2] For assessments in baseline window: if available prior to first trial drug intake, use the latest one of those. If only assessments available after first trial drug intake, use the one closest to the planned day as baseline value.

Table 6.7: 6 Time windowing rules for data from PedsQL questionnaire, 6MWT, Borg CR-10 scale®

Time window of actual day ^[1]			Allocated to		
Start day	End day (included)	Length of the time-window [days]	Visit number	Visit name	Planned day of the visit
-84	1	85	2	Baseline	1
2	267	266	6	24 weeks	169
268	463	196	9	52 weeks	365

[figure not shown]
^[1] First trial drug intake date is taken into account as reference to calculate time windows

This time windowing will be applied to the following data: PedsQL and 6MWT, Borg CR-10 scale

Table 6.7: 7 Time windowing rules for data from acceptability questionnaire

Time window of actual day ^[1]			Allocated to		
Start day	End day (included)	Length of the time-window [days]	Visit number	Visit name	Planned day of the visit
2	92	91	3	2 weeks	15
93	309	217	6	24 weeks	169

^[1] First trial drug intake date is taken into account as reference to calculate time windows

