| Statistical methods | 
Descriptive statistics will be provided for PK and safety endpoints. Analysis of secondary endpoints will be descriptive in nature using a mixed model with repeated measurements (MMRM) for continuous endpoints. Time-to-event endpoints will be displayed descriptively using the Kaplan-Meier method. Categorical endpoints, safety and tolerability will be displayed descriptively in frequency tables.
 |

FLOW CHART

| Trial Periods | Screening | | Treatment* | | | | | | | | | | | | | | | Follow-up |
|--|------------------------------------|---------------------|-------------------|-------|-------|-------|-----------|--------|-------------------|-----------|--------|-----------|--------|-----------|------------------|-----------|-------|---------------------|
| | | | Randomised Part A | | | | | | Open label Part B | | | | | | | | | |
| Visit | | 1 | 2 | 3 | 4 | 5 | 5a | 6 | 7 | 7a | 8 | 8a | 9 | 9a | X | Xa | EoT** | EoTrial*** |
| Weeks**** | | -4 | 0 | 2 | 6 | 12 | as needed | 24 | 26 | as needed | 36 | as needed | 52 | as needed | 52 plus Q12w | as needed | | |
| Days**** | Before or at the latest at Visit 1 | ≤28d before Visit 2 | D 1**** none | 15 ±3 | 43 ±3 | 85 ±3 | na | 169 ±3 | 183 ±3 | na | 253 ±7 | na | 365 ±7 | na | 365 plus Q84d ±7 | na | | EoT plus 28 days +3 |
| Informed consent and assent ¹ | X | | | | | | | | | | | | | | | | | |
| HRCT sent to central review ² | X | | | | | | | | | | | | | | | | | |
| Biopsy sent to central review (if required) ² | X | | | | | | | | | | | | | | | | | |
| Demographics | X | | | | | | | | | | | | | | | | | |
| Medical history | X | | | | | | | | | | | | | | | | | |
| Physical examination, Vital signs ³ | X | X | X | X | X | X | | X | X | | X | | X | | X | | X | X |
| Height (standing and sitting) ⁴ | X | X | X | | | X | | X | | | X | | X | | X | | X | (X) |
| Leg length | | | X | | | X | | X | | | X | | X | | X /Q24w | | X | |

| Trial Periods | Screening | | Treatment* | | | | | | | | | | | | | | | Follow-up |
|---|------------------------------------|---------------------|-------------------|----------|----------|----------|-----------|-----------|-------------------|-----------|-----------|-----------|-----------|-----------|------------------|-----------|-------|---------------------|
| | | | Randomised Part A | | | | | | Open label Part B | | | | | | | | | |
| Visit | | 1 | 2 | 3 | 4 | 5 | 5a | 6 | 7 | 7a | 8 | 8a | 9 | 9a | X | Xa | EoT** | EoTrial*** |

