| Potential risks of clinical relevance for this trial | Summary of data, rationale for the risk | Mitigation strategy |
|--|---|---|
| 
Potential risks in adults relevant to the paediatric population
 
 Gastrointestinal perforation | 
Based on mechanism of action and post-marketing data.
 | 
Increased awareness and expedite reporting (AESI).
 |
| 
Potential risks specific to the paediatric population, risk based on the nintedanib mechanism of action:
 
 Impact in maturation and growth | 
VEGFR blockade results in decreased angiogenesis, which is essential for growth and development processes.
 | 
Monitor potential effects on growth by: Height (standing and sitting) and leg length measurement every 12 weeks. Regular evaluation by SMC.
 |
| 
 Impact in bone development and growth | 
In animal models, nintedanib has been shown to alter the epiphyseal growth plates of large bones (femur and tibia). These changes were reported during bone growth, and were reversible after discontinuation.
 | 
Monitor potential reversible effects on bone development and growth by: Regular evaluation by radiology expert, with skeletal growth monitoring (MRIs or x-rays of epiphyseal growth plates) at baseline and follow-up in patients with open physes at 12, 24, 36, 52 weeks and every 24 weeks thereafter until end of the study or closure of the physes. Expedited reporting of pathological findings identified on bone imaging (AESI). Regular evaluation by SMC.
 |
| 
 Impact on dentition | 
In animal models, nintedanib has been shown to impact tooth development. Tooth changes were major with altered tooth structure and
 | 
Monitor potential severe/irreversible effects on dentition by: Regular evaluation by dentist, with dental examination at baseline and
 |

| Potential risks of clinical relevance for this trial | Summary of data, rationale for the risk | Mitigation strategy |
|--|---|---|

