- The site personnel will check the pregnancy test diary card (females only, and not to be done at Visit 4) and confirm that since the last scheduled visit at the site the pregnancy test has been repeated every 4-6 weeks until the current visit. If not confirmed, the investigator will re-instruct the patient and parent(s)/legal guardian. Test results will be documented in the patient's records. In case a positive test is reported the sponsor should be contacted immediately. Refer to [Section 3.3.4.1](#) for further instructions. Refer to [Section 5.2.7.2.3](#) for detailed information on event reporting in case of pregnancy.
- Adverse events, any ILD exacerbations, respiratory-related hospitalizations [REDACTED] and concomitant therapy since last visit will be reviewed and recorded.
- Prior to blood draw, physical examination including vital signs, weight, height, and leg length will be performed (height and leg length not planned at Visit 4; leg length planned every 24 weeks after the first year); data will be recorded in source documents and timely transferred per instructions provided (see ISF), to ensure central review as needed.
- The 12-lead ECG at rest will be conducted (if possible prior to blood draw), and evaluated by qualified personnel at site (Visit 6, Visit 9 and every 24 weeks after the first year only).
- SpO₂ measurement will be conducted on room air at rest.
- FVC measurement will be conducted according to procedures defined (see ISF for details).
- The 6-minute walk test including Borg CR-10 scale® and continuous pulse oximetry (SpO₂) will be conducted (Visit 6 and Visit 9 only).
- Blood and urine samples (safety laboratory tests, and pregnancy test on serum in female patients only) will be collected and submitted to the central laboratory.

- New medication wallets will be assigned by using the IRT system and dispensed, returned wallets will be collected as instructed (see ISF for details).
- Visit 6 only: The first dose of the open label trial medication will be administered at the site.
- Visit 6 only: The patient's acceptability questionnaire will be administered.

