5.2.2.3 N (%) of patients with treatment-emergent adverse events over the whole trial

The analysis will include all adverse events during the double-blind and open-label periods of the trial, see [Section 7.8.1](#).

5.2.2.4 Change in height, sitting height, leg length from baseline at week 24, and week 52, week 76, and week 100

The absolute change from baseline in height, the absolute change from baseline in sitting height and the absolute change from baseline in leg length will each be computed and evaluated separately.

As the sitting height has been measured incorrectly (i.e. total distance between the floor and the top of patient’s head with the patient in a sitting position) at some sites ([2](#)), the main analysis of this endpoint will contain only the correctly measured (i.e. total distance between the sitting surface and the patients top of patient’s head with the patient in a sitting position).

5.2.2.5 Change in Forced Vital Capacity (FVC) % predicted from baseline at week 24, and week 52

The absolute change from baseline in FVC % predicted (percent of predicted) at week 24 and week 52 will be used. The predicted values are calculated by the vendor according to Global Lungs Initiative (GLI) 2012 equations (4).

5.2.2.6 Absolute change from baseline in Pediatric Quality of Life Questionnaire (PedsQL) at week 24, and week 52

Health-related quality of life will be assessed using the PedsQL™ questionnaire. Depending on the age there are PedsQL™ Young Child Report (ages <8 years), Child Report (ages 8-12 years) and Report for Teens (ages >13.0 years). Furthermore, the respective Parent Reports are filled in by the parents of the child. For more details see CTP Section 5.6.1.

The questionnaire consists of 23 items and 4 dimensions: physical functioning, emotional functioning, social functioning and school functioning.

The PedsQL™ evaluation will primarily focus on the absolute change from baseline in the total score at week 24, and week 52.

In addition, the absolute change from baseline in the psychosocial health summary score (sum of emotional, social, and school functioning scales) and the absolute change from baseline in the physical health summary score (physical functioning score) will be presented.

A 5-point Likert response scale (0 = never; 1=almost never; 2=sometimes; 3=often; 4=almost always) is used in all cases except for the Young Child Report, where a 3-point scale (0=not at all; 2=Sometimes; 4=a lot) is used.

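### Week-64 and week-88 heights have no analysis window of their own, so when a week-52, week-76 or week-100 height is missing they can stand in for it, up to 84 days off target

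*SAP*

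**What the plan says.** **Measurement schedule.** In the protocol Flow Chart, the row "Height (standing and sitting) ⁴" has a plain X at Visit X, which is timed at "365 plus Q84d ±7". The leg-length row has an X restricted to every 24 weeks. Protocol 6.2.2 agrees: "leg length planned every 24 weeks after the first year". The risk table in Protocol 1.4.2 lists "Height (standing and sitting) and leg length measurement every 12 weeks" as the growth monitoring. It does not mention the later 24-week step for leg length, but on height it matches the Flow Chart.

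**Endpoint.** SAP 5.2.2.4 is "Change in height, sitting height, leg length from baseline at week 24, and week 52, week 76, and week 100". Protocol 2.1.3 has the same time points and warns that weeks 52, 76 and 100 will not exist for every patient.

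**Windows.** SAP 6.7 has a single table for both measures, "Table 6.7: 3 Time windowing rules for height and leg length". Its week-52 window is days 310 to 449, and the later rows step "Every 24 weeks thereafter". Weight is taken at the same Visit X but has 12-week steps (Table 6.7: 2).

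**Selection.** If two post-baseline records share a window, "then the measurement closest to the planned visit will be taken into account". If they are equally distant, the later one is used.

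**The concern.** Height is collected on a 12-week grid and analysed on a 24-week grid, and the edges of the wider grid fall exactly on planned visits. One day of scheduling decides whether the same visit belongs to one endpoint window or the next. A height with no analysis visit of its own is harmless while the endpoint height is there to displace it. It matters when the endpoint height is absent, and this design makes that common: Part B has variable length, and SAP 7.1 says patients will still be ongoing at the primary data cut.

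At stake is a growth-safety result. Protocol 1.4.2 names impaired growth as a potential paediatric risk. Height in a growing child rises with time, so a value taken up to 12 weeks from its label misstates the change from baseline at that label.

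**Working it through.** **Inputs.** Visit X days are 365 + 84k, with a tolerance of 7 days either side: week 64 = 449, week 76 = 533, week 88 = 617, week 100 = 701. Table 6.7: 3 uses planned day 365 and a step of 24 × 7 = 168.

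**Reproducing the SAP windows.** The edges are midpoints of planned days: (169 + 253)/2 = 211, (253 + 365)/2 = 309, (365 + 533)/2 = 449. These match the printed limits. Continuing the formula gives:

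| Window | Days | Planned day |
|---|---|---|
| Week 52 | 310–449 | 365 |
| Week 76 | 450–617 | 533 |
| Week 100 | 618–785 | 701 |

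**Where the in-between heights go.**
- Week 64 (days 442–456): 8 of the 15 tolerated days (442–449) fall in the week-52 window, 77 to 84 days after day 365. The other 7 (450–456) fall in the week-76 window, 83 to 77 days before day 533.
- Week 88 (days 610–624): 8 days (610–617) fall in the week-76 window, 77 to 84 days late. The other 7 (618–624) fall in the week-100 window, 83 to 77 days early.

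**Endpoint height present.** It lies within 7 days of its planned day, and the competitor is at least 77 days away. The endpoint height is selected in every combination of tolerated days.

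**Week-76 visit missed, weeks 64 and 88 attended.** There are 15 × 15 = 225 day combinations.
- Neither height falls in the window: 8 × 7 = 56.
- Only week 64 does: 7 × 7 = 49. Only week 88 does: 8 × 8 = 64.
- Both do: 7 × 8 = 56. The closer-value and tie rules give 28 to week 64 and 28 to week 88.
- Totals: week 64 is used in 77 (growth understated), week 88 in 92 (growth overstated), and week 76 is empty in 56.

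**Numbers at DBL 1.** Assume 30 children, uniform accrual over 18 months (78 weeks), a cut 26 weeks after the last patient, and visit days uniform over the tolerance. Follow-up is then uniform on 26 to 104 weeks.
- Week 76: true values 30 × (104 − 76)/78 = 10.8; late week-64 values 30 × (12/78) × (7/15) = 2.2. That is about 2 of 13.
- Week 100: true values 30 × (104 − 100)/78 = 1.5; late week-88 values 2.2 by the same formula. That is about 2 of 4.

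**Size per affected child.** If growth is steady from baseline, a value about 12 weeks early understates the change by about 12/76 = 16% at week 76 or 12/100 = 12% at week 100. A value about 12 weeks late overstates it by about 12/52 = 23% at week 52 or 16% at week 76.

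**DBL 2.** Children still on treatment have an EoT height. For a child whose follow-up ends between weeks 64 and 76, that height is closer to day 533 than the week-64 height and is selected. The error is then anywhere from 0 to 12 weeks. With 26 more weeks of follow-up (52 to 130, an assumption), 30 × 12/78 = 4.6 children per 30 end in that interval. About half, 2.3, have a week-76 value more than 6 weeks early, out of 30 × (130 − 76)/78 + 4.6 = 25.4 values (9%).

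**The case against.** The strongest reply is that the 24-week grid is deliberate. It matches the endpoint time points, neither document asks for a week-64 or week-88 height result, and the SAP uses the same grid for bone imaging and dental examination. Every visit stays in the listings, and the trial is descriptive, with no confirmatory testing. All of this stands. It makes the mismatch a weakness in the windowing, not a contradiction between documents.

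Three stronger readings are tempting, and the documents do not support them.
- A reader might infer that week-64 and week-88 heights are routinely analysed as week 76 and week 100. They are not. On their planned days they go backwards, and a present endpoint height always displaces them.
- A reader might infer that growth is always understated. That holds for loss at a data cut. For missed visits the error runs both ways.
- A reader might infer that the nintedanib arm would falsely show growth suppression. After week 24 all children are to receive nintedanib, so weeks 76 and 100 have no concurrent placebo group. Children who stop early are asked to attend later visits, where height is still measured (Protocol 6.2.3). Nothing in the documents indicates unequal stopping.

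The share at week 100 also looks alarming only as a percentage; it is about 2 of 4 children.

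**Conclusion.** The concern holds in a limited form. Week-64 and week-88 heights have no analysis visit, and they can fill a missing week-52, week-76 or week-100 value from up to 84 days away. The condition for this, a missing endpoint height, follows from variable follow-up and the DBL 1 cut, so it will arise. The window arithmetic comes from the documents. The counts rest on the assumed accrual and cut, and the percentages per child on steady growth, which will not hold for adolescents near final height. No between-arm bias is shown. This is a worthwhile, cheap correction to a secondary safety endpoint and not a threat to the trial's conclusions.

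**What to change.** For standing and sitting height, use the post-week-52 rule of Table 6.7: 2: week 52 = days 310–407, week 64 = 408–491, week 76 = 492–575, week 88 = 576–659, week 100 = 660–743. Keep Table 6.7: 3 for leg length only. Carry only the endpoint visits after week 52 into the by-visit tables and the MMRM, so that weeks 64 and 88 do not enlarge the unstructured covariance matrix.

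Every in-tolerance visit then sits inside its own window. After week 52 the largest mislabelling falls from 84 days to 42 (for week 76: 533 − 492 = 41 early, 575 − 533 = 42 late). It is not removed: an EoT height on days 492 to 532 is still labelled week 76. The early edge of the week-52 window, day 310, is unchanged.

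The cost is one SAP table and its programming, and slightly fewer values labelled week 52, week 76 and week 100. No new data or visits are needed.
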